Full Proposal

Study Title: Use of Dsuvia in Patients Undergoing Spine Surgery

Version Date:-10/28/2022

Background:

Dsuvia is a novel drug recently approved by the FDA (2018) for moderate to severe acute pain. It has a unique mode of delivery as a small sublingual tablet (Figure 1), and there is evidence to suggest it may provide significant benefit to surgical patients with moderate to severe pain. Based on published data as well as recently completed studies, there is strong evidence to suggest that DSUVIA can decrease other opioid consumption including long-acting opioids in major surgery, provide better pain control, and decrease PACU length of stay and earlier discharges.

Sufentanil, unlike morphine and hydromorphone, avoids the issue of active metabolites that can lead to prolonged, untoward effects, which can complicate postoperative care and affect patient discharge. A study by Minkowitz et al¹ found that sufentanil sublingual tablet (SST, Disuvia) 30 mcg was well tolerated, with no unexpected adverse events, no clinically meaningful vital sign changes, and a safety profile that was as expected for this postoperative patient population. In addition, Miner et al² studied the use of SST in the emergency department and found that SST was a potentially feasible option for managing moderate-to-severe acute pain in that setting. A study by Meijir et al³ studied adult patients undergoing major surgery in five hospitals in the Netherlands who received the SSTS for postoperative pain relief as part of multimodal pain management. The authors showed that the SSTS effectively managed postoperative pain in abdominal and orthopedic surgeries. A study by Melson et al⁴, a randomized, open-label

noninferiority study that enrolled patients scheduled for elective major open abdominal or orthopedic surgery assessed the proportion of patients who responded “good” or “excellent” at the 48-hour timepoint on the Patient Global Assessment (PGA48) of method of pain control. The results showed that 78.5% vs. 65.6% of patients achieved PGA48 “success” for SSTS vs. IV PCA morphine, respectively, demonstrating non-inferiority as well as statistical superiority for treatment effect. Patients using SSTS reported more rapid onset of analgesia and patient and nurse ease of care and satisfaction scores were higher than IV PCA morphine. Adverse events were similar between the 2 groups, and SSTS had fewer patients experiencing oxygen desaturations below 95% compared to IV PCA morphine. Future studies are needed to determine patient populations that benefit most from the SSTS, assess the added values versus intravenous patient-controlled analgesia, and determine the pharmacoeconomics of the system³.

More recently, a study by Cassavaugh K et al.⁵ analyzed data from a hospital comparing 140 DSUVIA-treated patients with 157 matched historical controls. DSUVIA was dosed either 30 minutes before the end of surgery for longer surgeries or just prior to induction for shorter surgeries. Patients were a combination of inpatient and outpatients (same-day surgery). The data shows an overall 56% decrease in PACU IV morphine milligram equivalents (mean MME \pm SE) opioid requirements compared to control group receiving typical IV opioids (8.1 ± 0.5 to 3.6 ± 0.4 ; $p < 0.001$). The PACU Phase 1 discharge time also was significantly decreased compared to the control group (80 ± 2 min vs 66 ± 2 min; $p < 0.001$). From a safety perspective, 3 patients out of 157 required naloxone in the PACU to reverse respiratory depression in the control group and no naloxone was required in the DSUVIA group. PACU time is estimated to cost between \$6-\$8 per minute, therefore the time saved more than pays for the drug and can increase efficiency and possibly caseload. The investigator’s conclusion is that DSUVIA is a high therapeutic index opioid that has an extended duration of action into the PACU period thereby either

avoiding opioids completely in the PACU in many patients (48.5% of patients in the DSUVIA group vs 16.6% of patients in the control group), or significantly decreasing the amount of IV opioids required in the PACU and therefore decreasing PACU discharge time.

Another recent study, by Tvetenstrand CD et al.⁶ was conducted in a hospital with ambulatory abdominal surgery patients with DSUVIA dosed 30 minutes prior to induction. A total of 47 patients were in the DSUVIA arm and 81 matched historical controls were compared. This study showed a decrease in overall IV opioid requirements and a decreased Phase 1 PACU time. No patients required naloxone for respiratory depression in either group.

Sufentanil is a drug with a rapid onset (15 min) and high potency (30 mg= morphine 5mg) (pka = 8.0 and solubility coefficient greater than 2000). It is highly bioavailable and highly lipophilic with a high therapeutic opioid index (LD50/ED50). It has a much lower Cmax compared with IV sufentanil. It reaches 70 % Cmax in 30 minutes, lasting as long as 3 hours. Based on existing outcomes data, we hypothesize that there will be a clinically significant difference in spine surgery patients as compared to the historical controls.

Purpose:

In this study we plan to examine the perioperative use of Dsuvia (sufentanil SL; FDA approval 2018) in the analgesic regimen for spine surgery, one of the most common surgeries performed in the US. Patients undergoing spinal fusion surgery often experience significant pain during the first three postoperative days⁷. Currently, no data are available for this patient population which routinely experiences moderate to severe acute pain requiring significant opioid use. We will analyze whether Dsuvia (sufentanil SL) is associated with lower pain scores, frequency of rescue

opioids, lower overall opioid consumption, PACU and hospital length of stay, and side effects of opioid use (i.e., nausea, vomiting, constipation, respiratory effects).

Hypotheses:

1. The perioperative use of Dsuvia 30 mcg SL in a prospectively recruited cohort of patients undergoing spine surgery will be associated with lower postoperative numeric rating scale pain scores (NRS; primary outcome) than observed in two historical control groups that did not receive Dsuvia: one group that received intraoperative remifentanil infusion and one that received intraoperative sufentanil infusion.
2. The perioperative use of Dsuvia (sufentanil SL) will be associated with lower overall opioid consumption, lower frequency of rescue opioids, lower PACU and hospital length of stay, and fewer side effects of opioid use (i.e., nausea, vomiting, constipation, respiratory complications) than observed in two historical control groups of patients receiving remifentanil or sufentanil infusions without perioperative Dsuvia.

Methods:

The study design is an Observational Longitudinal (OL) study with historical controls. There will be 1 prospectively recruited study arm (patients receiving the study drug Dsuvia) and 2 historical control arms (one that received an intraoperative remifentanil infusion and the other that received an intraoperative sufentanil infusion, both without Dsuvia).

Inclusion criteria:

[figure not shown]
Patients undergoing spine surgery (1-3 levels) who are opioid-naïve (no opioid use 30 days prior to surgery), 18-75 years old, ASA physical status 1-3.

Exclusion criteria:

Microdiscectomy, chronic opioid users, significant respiratory depression, acute or severe bronchial asthma, chronic lung disease, known or suspected gastrointestinal obstruction including paralytic ileus, liver disease (defined as alkaline phosphatase (ALP) > 56, aspartate aminotransferase (AST) > 100), known allergy or hypersensitivity to sufentanil or its components, baseline dementia, serotonin syndrome, adrenal insufficiency, severe hypotension, increased intracranial pressure, brain tumors, head injury, impaired consciousness, malignant hyperthermia, ASA physical status > 3, age > 75, pregnant patients.

IV. STUDY SCHEMA:

Patients undergoing spine surgery (1 or more levels)

Dsuvia 30mcg SL

Intraoperative Phase

General endotracheal anesthesia (TIVA with propofol/sufentanil)

Standardized anesthetic technique (see protocol below)

Dsuvia x1 prior to emergence from anesthesia

Postoperative Phase

Pain scores (NRS) q15 min up to 2 hrs

Concomitant Medication use/opioid consumption

Dsuvia prn q1hr as 1st line (NRS >3); Fentanyl prn as 2nd line, or 1st

line if repeat Dsuvia cannot yet be given and NRS is >3 (see PACU schema below)

Up to 3 doses of Dsuvia may be administered in the PACU (each at least 1 hr apart)

Hospitalization Phase

Follow up during inpatient hospital stay

Concomitant Medication use/pain scores

Both arms: standard of care analgesia (PO and IV prn)

Quality of Recovery (QoR); patient satisfaction (study arm only)

Post-discharge Phase

Follow up following discharge

Prescription opioid use

Outcomes:

Primary:

Mean postoperative pain scores (PACU)

Secondary:

Mean postoperative pain scores (inpatient)

opioid consumption (MMEs, PACU and inpatient)

Frequency of opioid rescue medications given

PACU LOS (min)

hospital LOS (days)

nausea, vomiting, constipation, respiratory events

sedation level (PACU)

quality of recovery (QoR 15)

utilization of prescription opioids following discharge

As shown above, the following secondary outcomes will also be collected in the Study cohort to obtain estimates that can be used to power future randomized controlled trials: sedation level, quality of recovery (QoR-15)⁸, patient satisfaction score (satisfaction with the level of pain control, 6-point scale⁴), and utilization of prescription opioids following discharge.

Safety assessments will include adverse events (AEs) and use of concomitant medications, periodic monitoring of vital signs (blood pressure, heart rate, and respiratory rate), and continuous monitoring of oxygen saturation in the PACU.

Detailed Clinical Protocol

Preoperative:

The surgeon will approach the patient and introduce the study and one of the investigators will explain the study to the patient. The surgeon will assess subject at their visit. At this visit, the surgeons will identify any patients that may benefit from Dsuvia. The information will be provided to one of the investigators. The investigator will subsequently review their eligibility and inclusion criteria. If the subject continues to meet all the criteria, the investigator will explain the study with the patient. Thereafter the patients will be provided the consent forms for their review and a 24/7 contact number for any questions regarding this study. All patient questions will be answered and informed consent will be obtained by one of the investigators who is a licensed physician listed on the protocol. The patient will be provided contact information. A co-investigator will be available to answer

questions on a 24 hour basis. It will be explained to the patient that they will be permitted to withdraw from the study at any time for any reason until their day of surgery. On arrival at the preoperative area, the patient will be assigned a code by one of the investigators. Prior to premedication, all patients will be made familiar with the use of numeric rating scale (NRS): 0-10 (no pain to the worst pain imaginable). The baseline NRS score will be recorded. All routine standard practices for surgery, anesthesia, and perioperative care will be followed with the exception of the study intervention. All patients will be premedicated with midazolam (0.025-0.05 mg/kg)

Intraoperative Management:

The Study arm will receive general endotracheal anesthesia (GETA). Anesthesia induction will be achieved with propofol (1.5-2.5mg/kg), succinylcholine (1mg/kg), and Fentanyl (50-100 mcg) bolus. Anesthesia maintenance will consist of TIVA (total intravenous anesthesia) with continued infusions of propofol (80-200 mcg/kg/min) and sufentanil (0.2-0.3mcg/kg/hr). The study group will receive Dsuvia 30 mcg at surgery end, administered by the anesthesiologist, timed to occur prior to emergence from anesthesia, and after the patient is turned supine. Antiemetic prophylaxis will be administered (ondansetron) per standard practice. The patient will then be transferred to the PACU.

Postoperative Management:

Note that Dsuvia will be ordered as q1hr prn, meaning that repeat doses must be administered at least 1 hr apart (up to 3 doses can be administered in the PACU).

Postoperative pain scores will be recorded by the PACU nurse and the research assistant. This will be obtained by using NRS scale every 15 mins up to 2 hours.

In the PACU, patients will be ordered to receive Dsuvia 30 mcg q1 hr prn for breakthrough pain (for NRS > 3) as the 1st line analgesic, with fentanyl as the rescue analgesic if the patient is still experiencing pain (NRS >3). The following opioid administration schema will be used for pain management in the PACU:

- 1st line: Dsuvia SL 30mcg (NRS >3). 2nd line: Fentanyl 25-50mcg (NRS >3)
- If upon arrival to the PACU the patient is still experiencing pain with NRS >3 but cannot yet receive a repeat dose of Dsuvia (because of having received 1st dose in the OR less than 1 hour ago), then the patient can receive fentanyl 25-50mcg prn until eligible to receive Dsuvia.
- If at any time the patient's NRS >3 after 20 min following an administration of either Dsuvia or fentanyl, the patient can receive a repeat dose of fentanyl until again eligible to receive Dsuvia.

Once the patient is transferred to the floor, both groups will receive the standard of care postoperative pain management orders (ie PO and IV prn analgesia for NRS > 3).

Patients who require additional doses of Dsuvia will be monitored for respiratory depression for at least one hour after the last administration of the drug dose.

Sample Size/Statistical analysis:

The primary outcome is nurse-collected mean pain scores. Assuming a within-group standard deviation in PACU NRS pain score of 2.5 points⁷, enrollment of 30 patients in the study group and inclusion of at least 80 patients in each retrospective control group will provide at least 80% power at a two sided alpha level of 0.025 (0.05/2 pair-wise comparisons) to detect a minimal clinically important difference of 2 points⁹ between the Study group and each of the retrospective groups using linear regression.

To account for any potential lack of comparability in baseline characteristics between patients in the Study and retrospective groups, all outcomes will be compared between the prospective group and each of the retrospective groups using doubly robust estimation incorporating both multivariable linear regression adjustment and inverse probability of treatment weights based on the propensity score¹⁰. Doubly robust estimation will allow for unbiased treatment effect estimates even if one of the two models (i.e., propensity score model or outcome model) is miss-specified. The multivariable linear regression models for the outcomes will adjust for the following covariates: age, sex, BMI, ASA class, surgical invasiveness tier, reoperation, history of anxiety, anxiolytic use, history of depression, and antidepressant use. Analytic weights will be based on the inverse of the propensity score, calculated via logistic regression as the probability of being in the Dsuvia group conditional upon the aforementioned covariates included in the multivariable outcome model.

Investigator Name/Institution:

[name], MS
Associate Professor of Anaesthesia
Director, Neuroanesthesia

Brigham and Women's Hospital
Harvard Medical School
Department of Anesthesiology, Perioperative and Pain Medicine
[name]
[name]
[contact]
Email: [contact]

Senior Project Manager:
[name]
Email: [contact]

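### The remifentanil contrast changes the infusion opioid and Dsuvia together, yet it is tested as a Dsuvia effect on a par with the sufentanil contrast, and no rule says whether one or both must succeed

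*Combined protocol and SAP*

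**What the plan says.** The Purpose section sets the aim: "We will analyze whether Dsuvia (sufentanil SL) is associated with lower pain scores". Hypothesis 1 compares pain after perioperative Dsuvia with "two historical control groups that did not receive Dsuvia: one group that received intraoperative remifentanil infusion and one that received intraoperative sufentanil infusion". Hypothesis 2 makes the same kind of claim for the secondary outcomes, "than observed in two historical control groups of patients receiving remifentanil or sufentanil infusions without perioperative Dsuvia". Methods repeats the two control arms: "one that received an intraoperative remifentanil infusion and the other that received an intraoperative sufentanil infusion, both without Dsuvia".

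The study arm's own infusion opioid is sufentanil. The Study Schema says so, and Intraoperative Management specifies "continued infusions of propofol (80-200 mcg/kg/min) and sufentanil (0.2-0.3mcg/kg/hr") before the Dsuvia tablet is given at the end of surgery.

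Sample Size/Statistical analysis treats the two contrasts identically. Each is tested at a "two sided alpha level of 0.025 (0.05/2 pair-wise comparisons"), and each is powered for a 2-point difference "between the Study group and each of the retrospective groups using linear regression". The propensity score is "calculated via logistic regression as the probability of being in the Dsuvia group", and the doubly robust result is described as an unbiased treatment effect if at least one of the two models is correct. The ten adjustment covariates describe the patient and the operation; infusion opioid is not among them. Neither contrast is named as the main one, and no success rule is given.

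**The concern.** In the remifentanil contrast, Dsuvia and the infusion drug are both fixed by group: all study patients have sufentanil plus Dsuvia, and all controls have remifentanil without it. A difference could come from the tablet, the infusion or both. The plan nevertheless attributes it to Dsuvia.

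The missing decision rule makes this worse. Hypothesis 1 can be read as requiring lower pain than in both control groups. Splitting 0.05 between two comparisons suggests instead two separate claims, either of which could stand alone. Under the second reading, a significant remifentanil contrast could be reported as a Dsuvia effect when it reflects the change of infusion. Under the first, a remifentanil contrast confounded in the opposite direction could block a real Dsuvia effect. If the rule is chosen after the results are known, the conclusion can follow the data.

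**Working it through.** **What each contrast estimates.** Let τ be the reduction in mean NRS due to Dsuvia. Let d be the excess pain of remifentanil over sufentanil infusion patients when neither has Dsuvia. Let b be the residual bias of a historical comparison.

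- Sufentanil contrast: τ + b.
- Remifentanil contrast: τ + d + b (b may differ between the two).

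Within the remifentanil contrast, an indicator for infusion drug is exactly one minus the indicator for study group. Adding it to the outcome model makes that model unidentifiable; adding it to the propensity model gives probabilities of 0 or 1. So d cannot be removed by either model, and double robustness does not help.

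**Inputs** (Sample Size/Statistical analysis): SD 2.5; 30 study patients; 80 per control group; difference 2; two-sided alpha 0.025 per contrast. The values of d, b and the variance inflation below are assumptions. The documents give neither the size nor the direction of d.

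**The plan's own figure.** SE = 2.5 × √(1/30 + 1/80) = 0.535, with 108 degrees of freedom. Noncentrality = 2/0.535 = 3.74. Power by noncentral t is 92.7% per contrast before weighting, consistent with the stated minimum of 80%. If weighting inflates the variance by 1.5 or 2 (SE multiplied by √1.5 or √2), power is 78.1% or 64.4%.

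**Dependence.** The contrasts share the 30 study patients, so their correlation is (1/30)/(1/30 + 1/80) = 0.727. The joint results below come from simulation (4,000,000 runs per case, shared study sample, separate pooled SD per contrast, no weighting).

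**No Dsuvia effect (τ = 0, b = 0), remifentanil controls with more pain by d:**

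| d (points) | Remifentanil contrast significant, two-sided | Either contrast favours Dsuvia | Both favour Dsuvia | Sufentanil contrast favours Dsuvia |
|---|---|---|---|---|
| 0 | 2.5% | 2.1% | 0.4% | 1.25% |
| 0.5 | 9.5% | 9.7% | 1.0% | 1.25% |
| 1.0 | 34.7% | 34.7% | 1.2% | 1.25% |
| 1.5 | 70.1% | 70.1% | 1.2% | 1.25% |

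Counting significance of either contrast in any direction, the rates at d = 0.5, 1.0 and 1.5 are 10.9%, 35.9% and 71.3%.

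**True 2-point Dsuvia effect (τ = 2, b = 0), remifentanil controls with less pain:**

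| Less pain by (points) | Both contrasts favour Dsuvia | Sufentanil contrast favours Dsuvia |
|---|---|---|
| 0 | 88.6% | 92.7% |
| 0.5 | 69.2% | 92.7% |
| 1.0 | 34.6% | 92.7% |
| 1.5 | 9.4% | 92.7% |

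**The sufentanil contrast is not immune.** The 1.25% needs b = 0. An assumed residual bias of 0.5 or 1.0 point towards Dsuvia raises it to 9.4% or 34.7%. Such bias is plausible: the controls are historical, their infusion dose and PACU regimen are not given, and the Preoperative section has surgeons pick out patients who may benefit from Dsuvia. What this contrast avoids is d.

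**The case against.** The strongest reply is that the plan hides nothing. It names both controls by infusion drug, analyses them separately, calls the study observational and words its hypotheses as associations. The same-infusion comparator is already there and adequately powered before weighting. The alpha split controls type I error: with both nulls true, the chance of any significant contrast is about 4.2%. At the planned 2-point difference in both contrasts, 30/80/80 exceeds 80% power under either rule, again before weighting. All of that is right, so this is not an alpha or sample-size error. It does not answer the point. An association with Dsuvia is still what the remifentanil contrast is said to show, and the analysis section calls the estimate a treatment effect.

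It is also fair that d is assumed, that the false-claim and veto scenarios need opposite signs of d and so cannot both apply, and that equal bias would mislead the sufentanil contrast just as often. The tables therefore illustrate how much hangs on the unstated rule; they do not predict this study's error rate.

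Finally, if one contrast decides, testing it at 0.025 costs power: at variance inflation 1.5 or 2, 78.1% or 64.4% against 85.6% or 74.5% at 0.05. This stands as a cost. Keeping the split is a valid conservative choice while both contrasts are still reported as claims.

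**Conclusion.** The concern holds, with high confidence, and should be fixed. That the remifentanil contrast cannot isolate Dsuvia follows from the arm definitions alone and needs no assumption about d. The absence of a decision rule is likewise plain from the text.

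The size is conditional. For an assumed infusion difference of 0.5 to 1.5 points, the wrong-claim rate runs from 9.7% to 70.1% if either contrast suffices, against at most 1.2% if both are needed. With a difference of the same size in the other direction, requiring both cuts power for a 2-point effect to between 69.2% and 9.4%. These figures assume SD 2.5, 30 against 80, no weighting and no residual bias in the sufentanil contrast. That contrast is the closer comparator because it holds the infusion drug constant, but it remains historical and non-randomised.

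A secondary point, held with moderate confidence and not needed for this conclusion: baseline NRS is recorded in the study arm (Preoperative section) but is in neither the outcome nor the propensity model. The documents do not say whether controls have a comparable score.

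**What to change.** Add to Hypotheses 1 and 2 and to Sample Size/Statistical analysis:

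> A conclusion about Dsuvia rests on the contrast with the sufentanil-infusion group, which is historical and non-randomised. The contrast with the remifentanil-infusion group is reported as regimen v regimen (sufentanil infusion plus Dsuvia v remifentanil infusion). It can neither establish nor veto a Dsuvia effect on its own.

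Report the sufentanil controls' infusion dose and PACU opioid regimen beside those of the study arm, so that readers can judge how closely that control matches.

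Secondary: where a comparable preoperative NRS is charted for controls, add it to both models. If it is often missing, by a threshold set before outcomes are abstracted, report the baseline-adjusted analysis as a sensitivity analysis.

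Cost: two or three sentences, with no change to arms, sample size or alpha. The downsides are a weaker claim for the remifentanil contrast and a Dsuvia conclusion that rests on one historical group of unknown residual bias. The secondary item needs one more abstracted field, which may be missing in controls or not comparable with a score taken after patients have been taught the scale.

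### The historical controls have no stated period, source or sampling order, and calendar time is in neither model, so the promise of unbiased estimates is an overclaim

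*Combined protocol and SAP*

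**What the plan says.** **Design (Methods).** The study is an "Observational Longitudinal (OL) study with historical controls". Besides the prospective Dsuvia arm there are "2 historical control arms (one that received an intraoperative remifentanil infusion and the other that received an intraoperative sufentanil infusion, both without Dsuvia". The inclusion criteria follow under the same heading: "Patients undergoing spine surgery (1-3 levels) who are opioid-naïve (no opioid use 30 days prior to surgery), 18-75 years old, ASA physical status 1-3". They are neither restricted to the study arm nor expressly extended to the controls.

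**Entry to the study arm (Detailed Clinical Protocol, Preoperative).** At the clinic visit "the surgeons will identify any patients that may benefit from Dsuvia"; an investigator then checks eligibility and obtains consent. No corresponding step is described for controls.

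**Analysis (Sample Size/Statistical analysis).** "The primary outcome is nurse-collected mean pain scores". The calculation begins "Assuming a within-group standard deviation in PACU NRS pain score of 2.5 points" and pairs 30 study patients with "inclusion of at least 80 patients in each retrospective control group", for at least 80% power to detect 2 points at two-sided alpha 0.025 per contrast. Every outcome is to be compared by weighted regression. The outcome and propensity models use the same ten covariates: age, sex, BMI, ASA class, invasiveness tier, reoperation, and history and drug treatment of anxiety and of depression. The plan then says: "Doubly robust estimation will allow for unbiased treatment effect estimates", even when one of the two models is wrong.

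**Not stated anywhere.** There is no calendar period for the controls, no data source, no consecutive, random or matched sampling rule, no time-trend sensitivity analysis, and no condition on unmeasured confounding or overlap.

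**The concern.** A prospective arm set against historical controls differs from them in calendar time as well as in treatment. If multimodal analgesia, surgical technique or PACU practice changed between the two periods, pain scores would change whether or not Dsuvia works. The planned adjustment cannot see that change, because nothing in either model carries it.

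Double robustness is a statement about model form: given that the covariates suffice to control confounding and the groups overlap, only one of the two models need be correct. It offers nothing against a variable omitted from both. A reader who takes the sentence at face value would treat the Dsuvia coefficient as free of era effects.

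The missing period and sampling order make this worse in two ways. Nobody can judge how far apart in time the arms are, or whether the two control groups come from the same years. And control outcomes already exist when the controls are chosen, so without a fixed rule the plan cannot show that the choice was independent of them.

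**Working it through.** **Inputs.** From Sample Size/Statistical analysis: SD 2.5, n = 30 and 80, difference 2 points, two-sided alpha 0.025 per contrast (critical value 2.241). The drift sizes are assumptions; the documents give none.

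**1. The plan's own figure.** SE = 2.5 × √(1/30 + 1/80) = 0.535. Power = Φ(2/0.535 − 2.241) = 93.3% (92.7% with the noncentral t, 108 df). This satisfies at least 80%, so the sample-size statement is not in error.

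**2. Effect of an uncorrected drift b when the drug does nothing.** P(reject) = Φ(b/SE − 2.241) + Φ(−b/SE − 2.241).

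| Drift b (NRS points) | b/SE | P(reject) per contrast | Multiple of 2.5% |
|---|---|---|---|
| 0 | 0 | 2.5% | 1 |
| 0.25 | 0.467 | 4.1% | 1.7 |
| 0.5 | 0.934 | 9.6% | 3.9 |
| 1.0 | 1.868 | 35.5% | 14 |

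With the t distribution, the last two rates are 9.5% and 34.7%.

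**3. Does the planned estimator remove the drift?** In 2,000 simulated trials of 30 against 80, with three illustrative covariates and both models correct for them, inverse-probability-weighted regression returned mean estimates of 0.00, −0.50 and −1.00 for drifts of 0, 0.5 and 1.0 points towards lower pain. The whole drift appears as treatment effect. Rejection rates were 3.1%, 8.9% and 30.6%.

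**4. Sensitivity to weighting.** If weighting cut the effective sample size to 60% (an assumption), SE = 0.535/√0.6 = 0.691. The rates at 0.5 and 1.0 points would then be 6.6% and 21.4%. The bias itself is unchanged; only its visibility against noise falls.

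**5. Two contrasts, one study arm.** Both contrasts use the same 30 patients (correlation (1/30)/(1/30 + 1/80) = 0.727). If both control groups share the drift, the chance of at least one false positive is 4.2% with none, 14.6% at 0.5 points and 46.6% at 1.0. Agreement between the contrasts is therefore weak corroboration.

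**6. Direction.** Drift towards lower pain falsely favours Dsuvia. Drift of 0.5 points the other way reduces a true 2-point effect to an apparent 1.5, and power to Φ(1.5/0.535 − 2.241) = 71%.

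**7. Can the controls reveal the drift?** With 160 pooled controls spread evenly over a window, the SE of the fitted change over half the window is 2.5 × √12 / (2 × √160) = 0.34. A 0.5-point change would be detected at two-sided 0.05 with power of about Φ(0.5/0.342 − 1.96) = 31%.

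**The case against.** Several stronger readings are tempting, and the documents do not support them.

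- *That any 80 past patients would qualify.* The eligibility criteria sit under the same heading as the three-arm description and most naturally cover the controls, who are also defined by infusion and absence of Dsuvia. What is missing is narrower: period, source and sampling order.
- *That controls will be picked with their outcomes in view.* Nothing describes discretionary choice, and a minimum of 80 is compatible with taking every eligible patient. The point is only that no rule excludes such choice.
- *That time cannot be modelled at all.* If the arms do not overlap in time, it fails in the propensity model. A trend in the outcome model can still be estimated among controls and extrapolated, if one accepts that it continued. Complete non-overlap is itself inferred from the word historical; no dates are given.
- *That the trial's false-positive rate is 10% or 35%.* Those figures follow from assumed drifts and an unweighted SE. One point is half the plan's clinically important difference, and at 0.25 points the inflation is less than twofold.

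It is also fair to say that the design is declared openly, that the hypotheses speak of association, and that the method is introduced to deal with differences in baseline characteristics. Read in that setting, the unbiasedness sentence is the usual textbook description with its conditions left out. That softens the criticism but does not answer it: the omitted conditions are the ones a historical comparison is least able to meet.

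**Conclusion.** The concern holds in this form: the plan omits the controls' period, source and sampling order, leaves calendar time out of both models, and claims an unbiasedness that double robustness cannot supply against a confounder missing from both. That much rests on the text alone.

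The size of the harm is not known. On the plan's SD and sample sizes, illustrative drifts of 0.25, 0.5 and 1.0 points give about 4%, 10% and 35% per contrast against 2.5%, less if weighting costs effective sample size. Neither the magnitude nor the direction of any drift can be read from the documents. The choice of estimator is reasonable. This should be changed before control data are extracted, because it affects what a significant result may be taken to show.

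**What to change.** 1. **Fix the control sample.** State the data source and that the same eligibility criteria apply to controls. Take all consecutive eligible patients working backwards from the first Dsuvia enrolment, in one common calendar window where feasible, until each group has at least 80.
2. **Pre-specify a tipping-point analysis** for each contrast, giving the drift that would remove the result: |estimate| − 2.241 × SE. For example, an observed 2-point difference with SE 0.535 would lose significance at a drift of 2 − 1.20 = 0.80 points. Report the within-control calendar trend beside it as an estimate with a confidence interval. It should not be a pass/fail test, because its low power means that a null result could falsely reassure.
3. **Correct the unbiasedness sentence.** Limit it to confounding by the measured covariates, assuming no unmeasured confounding (including era) and adequate overlap.

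**Cost.** Protocol wording and one additional analysis, with no new patients to recruit. There is less freedom in choosing controls. The window may have to extend for the rarer infusion, and a longer window can itself admit more drift, so its dates should be reported for each group. Era confounding is reduced and quantified, not removed.
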